6.3 Rationale for Study Design and Endpoints

In order to maximize the scientific value of the study and minimize the risk for systemic biases, a parallel group, double-blind, randomized design will be utilized.

The study will recruit subjects with hyperuricemia and a diagnosis of gout per American College of Rheumatology (ACR) criteria ([Neogi et al 2015](#)) ([Appendix A](#)). To participate in the study, subjects will be required to meet the inclusion criterion of sUA ≥ 8.0 mg/dL to ≤ 12.0 mg/dL during the 9 to 4 days prior to the treatment period. To reduce potential safety issues, subjects will be required to have adequate renal function based on an estimated glomerular filtration rate (eGFR) ≥ 60 mL/min/1.73m² at screening (Visit 1) and no evidence of medically significant comorbidities.

Patients with gout may experience an acute gout flare event with initiation or an increase in their dose of ULT ([Becker et al 2005a](#); [Becker et al 2010](#); [Borstad et al 2004](#)). Consequently, all enrolled subjects will receive gout flare prophylaxis with colchicine from Visit 2 (between Days -30 to -23) through to the end of treatment in accordance with recommendations from the European League Against Rheumatism (EULAR), ACR, and British Society of Rheumatology treatment guidelines ([White et al 2018](#); [Zhang et al 2006](#); [Jordan et al 2007](#); [Khanna et al 2012a](#); [Khanna et al 2012b](#)).

The primary endpoint in the study will be the proportion of subjects achieving a sUA level < 5.0 mg/dL at Day 84 for LC350189, while a key secondary endpoint is the proportion of subjects achieving a sUA level of < 6.0 mg/dL at Day 84 for LC350189. These endpoints were chosen to align with the ACR goals for ULT, which include achieving a sUA < 6 mg/dL in all gout patients and a sUA < 5 mg/dL in patients with palpable tophi detected by physical examination ([Khanna et al 2012a](#)). These are also standard endpoints frequently used in Phase II intervention trials in hyperuricemia and gout ([Gunawardhana et al 2018](#)).

As another secondary endpoint, gout flare rate will be captured by eDiary on a background of prophylaxis; gout flares will be defined according to a previous Phase II study ([Neogi et al 2015](#); [Poiley et al 2016](#)). Safety endpoints used in this study, including AEs, clinical laboratory values, vital signs, and ECG, conform to accepted clinical and laboratory assessments of subjects participating in clinical trials and are typical of a Phase II study. Additional exploratory assessments (HbA1c, fasting plasma glucose [FPG], high-sensitivity C-reactive protein [hs-CRP], serum concentrations of hypoxanthine and xanthine) will be included to inform subsequent studies in the LC350189 clinical development program.

6.4 Study Discontinuation and Stopping Criteria

6.4.1 Criteria for Premature Termination or Suspension of Study

The study will be completed as planned unless one or more of the following criteria are satisfied that require temporary suspension or early termination of the study.

- New information or other evaluation regarding the safety or efficacy of the investigational product that indicates a change in the known risk/benefit profile for the compound, such that the risk/benefit is no longer acceptable for subjects participating in the study.
- Significant violation of Good Clinical Practice (GCP) that compromises the ability to achieve the primary study objectives, or compromises subject safety or data integrity.

6.4.2 Criteria for Premature Termination or Suspension of Investigational Sites

Premature termination or suspension of investigational sites will occur if any of the following criteria are satisfied:

- Failure to meet expected enrollment goals.
- Administrative reasons.

In the event that the Sponsor, an institutional review board (IRB)/ independent ethics committee (IEC), or regulatory authority elects to terminate or suspend the study or the participation of an investigational site, a study-specific procedure for early termination or suspension will be provided by the Sponsor. The procedure will be followed by applicable investigational sites during the course of termination or study suspension.

6.4.3 Criteria for Early Termination of Individual Subjects

Subjects (or their guardians, or legally acceptable representatives) may withdraw their consent to participate in the clinical study. If a subject (or their guardians, or legally acceptable representatives) withdraws consent, the date and reason for consent withdrawal should be documented. Subjects will be encouraged to continue all study assessments. Subject data will be included in the analysis up to the date of the consent withdrawal, unless otherwise indicated by the Sponsor. If the subject refuses to continue all study procedures, they should undergo a 2-week safety follow-up period per study design.

Early termination will also occur if any of the following conditions apply:

- AE or SAE that requires discontinuation at the discretion of the Investigator.
- Subject becomes pregnant or begins breastfeeding (mandatory).
 - Administration of investigational product should be discontinued immediately after pregnancy is confirmed, and the Sponsor should be notified within 24 hours. Information on the subject, the pregnancy and its outcomes, and information on the infant's status at 12 weeks after delivery, if applicable, should be obtained.
- Unexplainable elevations in liver enzymes. Subjects should be monitored until all abnormal values return to normal or baseline values, and the outcomes should be recorded in the eCRF.
 - Subjects should discontinue the investigational product immediately if alanine aminotransferase (ALT) or aspartate aminotransferase (AST) elevations are ≥ 8 times the upper limit of normal (ULN) at any time during the clinical study.
 - If ALT or AST elevations are ≥ 5 times ULN at any time during the clinical study, laboratory tests should be repeated within 3 days. If elevations ≥ 5 times ULN are confirmed, subjects should discontinue the investigational product.
 - Subjects should discontinue the investigational product if ALT or AST are elevated ≥ 3 times ULN in combination with laboratory finding of either total bilirubin is ≥ 2 times ULN or international normalised ratio of prothrombin time (INR) is ≥ 1.5 times ULN at any time during the clinical study.
 - Subjects should discontinue the investigational product immediately if ALT or AST are elevated ≥ 3 times ULN and clinical symptoms (fatigue, nausea, vomiting, right upper quadrant pain or tenderness, fever, rash, and/or eosinophilia [$>5\%$]) are present at any time during the clinical study.
- Subjects with serum creatinine elevations at any visit >1.5 times baseline level will be closely monitored. If serum creatinine elevations are >2.0 times compared to baseline, and if this observation cannot be explained by concomitant disease or another alternative etiology, subjects should discontinue the investigational product.
- Treatment will be interrupted in subjects presenting with signs or symptoms that may indicate acute UA nephropathy including flank pain, urine color change, nausea, or vomiting; in these cases, serum creatinine will be promptly measured. Subjects should discontinue the investigational product.
- Lost to follow up. The subject did not return to the clinic and attempts to contact the subject were unsuccessful. Attempts to contact the subject must be documented.
 - Subjects are not required to provide reasons for not attending study visits; however, Investigators should make an effort to identify the pertinent reasons while respecting the subject's rights. Available information should be recorded in the eCRF.
- Protocol violation: If protocol violation occurs, which, in the clinical judgment of the Investigator or after discussion with the Sponsor, may invalidate the study by interfering

pharmacokinetically or pharmacodynamically with the investigational product(s), or affect the safety of the subject, the subject will be withdrawn by the Investigator.

- Subject conduct or any other events, which, in the clinical judgment of the Investigator or after discussion with the Sponsor, may invalidate the study.
- Study discontinuation by the Sponsor.

Wherever possible, the tests and evaluations, including those listed for the follow-up Visit (Visit 9), should be performed for all subjects who discontinue prior to completion of the study.

In the event the Investigator determines to terminate a subject's participation in the clinical study, the Investigator must notify the Sponsor of such decision and rationale immediately in writing.

7.0 STUDY POPULATION

7.1 Inclusion Criteria

1. Subjects or the subject's legally acceptable representatives who sign a written ICF prior to the initiation of any study procedures.
2. Male or female subjects between the ages of 18-75 years, inclusive.
3. Subjects with hyperuricemia and a history or presence of gout per ACR criteria ([Appendix A](#)) ([Neogi et al 2015](#)).
4. Subjects with a self-reported history of ≥ 2 gout flares in the prior 12 months to screening (Visit 1).
5. Subjects who are currently on urate lowering therapy (ULT; Allopurinol, Febuxostat, Probenecid, Lesinurad) with a sUA level ≥ 6.0 mg/dL at Visit 1; Or subjects who are ULT naïve or currently not on ULT with a sUA level ≥ 8.0 mg/dL to ≤ 12.0 mg/dL at Visit 1.
6. Subjects with a sUA level ≥ 8.0 mg/dL to ≤ 12.0 mg/dL at Day -9 to -4 (Visit 3).
7. Subjects with a body mass index (BMI) ≤ 42 kg/m² at screening (Visit 1).
8. Subjects with eGFR ≥ 60 mL/min/1.73m² at screening (Visit 1).
9. For childbearing subjects, a negative pregnancy test result at screening (Visit 1). Subjects (female subjects of childbearing potential and male subjects with partners of childbearing potential) must agree to use proper contraceptive methods to avoid pregnancy during the study.
10. Subjects who are capable of understanding the study procedures, the risks involved, and are willing to adhere to the visit/protocol schedule.

7.2 Exclusion Criteria

1. Subjects with secondary hyperuricemia (*e.g.*, due to myeloproliferative disorder, or organ transplant).
2. Subjects experiencing an active acute gout attack within 3 weeks prior to screening (Visit 1).
3. Subjects with AST or ALT >2 times ULN at screening (Visit 1).
4. Subjects with creatine kinase >2.5 times ULN at screening (Visit 1).
5. Subjects with previous intolerance to colchicine.
6. Subjects who received pegloticase within 3 months prior to screening (Visit 1).
7. Subjects who have not been receiving stable doses of drugs known to affect sUA levels (losartan, fibrates, thiazide diuretics, loop diuretics, acetylsalicylic acid [ASA]) for the last six weeks prior to screening (Visit 1). ASA use more than 325 mg/day is not allowed.

8. Subjects who have received systemic corticosteroids more than 10 continuous days within 1 month prior to screening (Visit 1).
9. Subjects who require or may require systemic immunosuppressive or immunomodulatory treatment (eg, azathioprine, 6-mercaptopurine, cyclosporine).
10. Subjects receiving medications that are strong or moderate CYP3A4 inhibitors or P-glycoprotein (P-gp) inhibitors within 14 days prior to screening (Visit 1).
11. Subjects with a history of xanthinuria.
12. Subjects with a history of rheumatoid arthritis.
13. Subjects with active peptic ulcer disease requiring treatment.
14. Subjects with unstable angina, New York Heart Association (NYHA) class III or IV heart failure, myocardial infarction, stroke, deep venous thrombosis (DVT), percutaneous coronary intervention (with or without stent), or coronary artery bypass graft (CABG) in the last 12 months prior to screening (Visit 1); Subjects currently receiving anticoagulants; Or subjects with clinically significant ECG abnormality in the opinion of the Investigator at screening (Visit 1).
15. Subjects with uncontrolled hypertension (systolic pressure above 160 mmHg or diastolic pressure above 95 mmHg) at screening (Visit 1).
16. Subjects with a history of myositis/myopathy, rhabdomyolysis, Stevens-Johnson syndrome, or toxic epidermal necrolysis.
17. Subjects with a history of malignancy within the previous 5 years with the exception of non-melanoma skin cancer that has been treated with no evidence of recurrence, treated cervical dysplasia, or treated in situ Grade 1 cervical cancer.
18. Subjects with known hypersensitivity or allergy to any ingredients of LC350189.
19. Subjects that consume more than 14 drinks of alcohol per week (e.g., 1 drink = 5 oz [150 ml] of wine, 12 oz [360 ml] of beer, or 1.5 oz [45 ml] of hard liquor).
20. Subjects with a history or suspicion of drug abuse (defined as any illicit drug use) within the past 5 years.
21. Subjects who are pregnant or lactating.
22. Subjects who test positive for human immunodeficiency virus (HIV) or active hepatitis B or hepatitis C virus (HCV) infection. Active HCV infection is defined as a subject with a positive hepatitis C antibody and detectable hepatitis C viral load RNA.
23. Subjects who have previously participated in interventional clinical studies within 3 months or 5 half-lives of investigational therapy (whichever is longer) prior to the screening visit (Visit 1).
24. Subjects with any other medical or psychological condition, which in the opinion of the Investigator and/or Medical Monitor, might create undue risk to the subject or interfere

with the subject's ability to comply with the protocol requirements, or to complete the study.

7.3 Prohibited or Precaution Medications / Food

Use of the agents listed in [Table 7-1](#) (prescription or nonprescription) is prohibited or with precaution from the time points specified until completion of all study activities.

Table 7-1 Prohibited or Precaution Medications / Food

Medication or Class / Food	Noted or anticipated outcome	From time point specified
Prohibited Medications/Food		
Allopurinol, Febuxostat*	Urate-lowering drug; Potential interference with study related outcome measures – sUA levels.	Wash-out/prophylaxis period (Visit 2)
Lesinurad		
Uricosuric agent (Probenecid, Sulfinpyrazone)		
Atazanavir, Clarithromycin, Indinavir, Itraconazole, Ketoconazole, Nefazodone, Nelfinavir, Ritonavir, Saquinavir, Telithromycin, Darunavir/Ritonavir, Lopinavir/Ritonavir, Tipranavir/Ritonavir	Strong CYP3A4 inhibitors; Potential PK interaction with prophylactic medication.	Screening (Visit 1)
Amprenavir, Aprepitant, Diltiazem, Erythromycin, Fluconazole, Fosamprenavir, Grapefruit, grapefruit related citrus fruits and their juices, Verapamil	Moderate CYP3A4 Inhibitors; Potential PK interaction with prophylactic medication.	Screening (Visit 1)
Cyclosporine, Ranolazine	P-gp inhibitors; Potential PK interaction with prophylactic medication.	Screening (Visit 1)
Theophylline, Azathioprine, 6-Mercaptopurine	XO substrate; Potential PK interaction with investigational products.	Screening (Visit 1)
Systemic corticosteroid (Prednisone >10 mg/day or its equivalent; Or prednisone ≤10 mg/day or its equivalent for more than 7 days)	-	Screening (Visit 1)
Precautions		
HMG-Co A Reductase Inhibitors: Atorvastatin, Fluvastatin, Lovastatin, Pravastatin, Simvastatin	Potential PK interaction with prophylactic medication, Increase risk for muscle-related toxicity when administer with prophylactic medication.	Screening (Visit 1)
Other Lipid Lowering Drugs: Fibrates, Gemfibrozil		
Digitalis glycosides: Digoxin	Potential PK interaction with prophylactic medication; Increase risk for muscle-related toxicity when administer with prophylactic medication.	Screening (Visit 1)

* Not applicable to the subjects randomized to the active control group before the implementation of the Protocol version 5.0.

Subjects will continue taking any other medications prescribed for chronic conditions at stable dose from screening (Visit 1) to Day 84 (Visit 8), with the exception of those listed above. Females will be permitted to use hormone replacement therapy.

Subjects will refrain from receipt of any other investigational drug within 5 half-lives or 90 days, whichever is longer, prior to study entry and during the entire study. Females of childbearing potential will refrain from using hormonal contraception.

During participation in the study, subjects will be instructed not to take any prescription medications without first consulting the Investigator.

Any medication taken by a subject during the course of the study and the reason for its use will be documented in the source documents and the eCRF.

8.0 STUDY MATERIALS

8.1 Investigational Products

8.1.1 LC350189

LC350189 50, 100, or 200 mg will be supplied by LG Chem, Ltd. as hard gelatin capsules with StarCap 1500 and magnesium stearate.

8.1.2 Placebo

Placebo will be supplied as capsules identical in appearance to the LC350189 capsule.

8.2 Packaging, and Labeling of Investigational Products

The Sponsor or a Sponsor-designated third party will provide the Investigator with the labeled investigational products in accordance with specific country regulatory requirements.

8.3 Storage and Drug Accountability of Investigational Products

All clinical material must be kept in an appropriate, limited-access, secure location.

The investigational products and their storage and preparation instructions will be provided by the Sponsor. All investigational products will be stored at room temperature. Investigational products should not be exposed to excessive heat or direct sunlight.

The study staff is required to document the receipt, dispensing, and return/destruction of investigational products and supplies provided by or on behalf of the Sponsor.

The Investigator or Investigator's authorized staff must ensure the availability of proper storage conditions. The temperature of all investigational products will be monitored 24 hours a day, 7 days a week (24/7). In case of incorrect storage, the Sponsor and monitor must be contacted without delay.

No investigational products may be dispensed to any person not enrolled in the study.

8.4 Dose Regimen

Subjects will receive LC350189 50 mg, LC350189 100 mg, LC350189 200 mg, or placebo. LC350189 or placebo capsules will be packaged in 60 mL bottles, each containing 35 capsules. On Day 1 (Visit 4), the appropriate investigational product per the randomization code will be dispensed. Additional bottles will be dispensed on Day 28 (Visit 6) and Day 56 (Visit 7). At visits where investigational product is being returned and new investigational product is being dispensed, all bottles should be returned for investigational product accountability. In order to facilitate investigational product accountability, the subjects ID as well as the visit number must be filled in on the label before dispensing.

Subjects will self-administer investigational product (two capsules of LC350189/placebo) and one tablet of gout flare prophylaxis orally once daily in the morning, if possible, at approximately the same time each day, with water and without regard to food.

Subjects will self-administer investigational product from the following bottles:

- Subjects randomized to LC350189 50 mg will self-administer one capsule from each of 2 bottles of LC350189 25 mg.
- Subjects randomized to LC350189 100 mg will self-administer one capsule from each of 1 bottle of LC350189 100 mg and 1 bottle of LC350189 placebo.
- Subjects randomized to LC350189 200 mg will self-administer one capsule from each of 2 bottles of LC350189 100mg.
- Subjects randomized to placebo will self-administer one capsule from each of 2 bottles of LC350189 placebo.

Subjects will be instructed to stay adequately hydrated. On Day 1 (Visit 4), investigational product will be taken at site from the bottle handed out at the visit. On Day 14 (Visit 5), investigator product will be taken at site from the bottle dispensed on Day 1 (Visit 4). On Day 28 (Visit 6) and 56 (Visit 7), investigational product will be taken from the bottle newly dispensed and handed out at the visit.

8.4.1 Compliance

The administration of investigational products will be recorded in the appropriate sections of the eCRF. During the study, subjects will receive a total of 2 bottles for LC350189/ placebo. Subjects who are randomized to the study groups before the implementation of the Protocol version 5.0 will continue receiving a total of 3 bottles for LC350189/febuxostat/placebo. Subjects will be required to bring investigational product containers to each clinic visit, regardless of whether the investigational product container is empty. If a patient is persistently noncompliant with an investigational product, (taking <80% or >120% of the allocated investigational product for the period since the last visit) it may be appropriate to withdraw the subject from the study. All subjects should be re instructed about the dosing requirement during study visits. Compliance will be measured using the following formula:

$$\begin{aligned}(B) \div (C) &= (D) \\ (D) \times 100 &= \% \text{ Compliance}\end{aligned}$$

Where (B) = the total number of capsules minus the number of capsules in the bottle and (C) = the number of days during treatment period.

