--	--

Table 2-1 Schedule of Assessments

Study Period ¹	SCREENING & WASH-OUT/PROPHYLAXIS ²			TREATMENT PERIOD ³				End of treatment/ early termination	FOLLOW-UP
				—					
Visit number	1	2	3	4	5	6	7	8	9
Time point (Weeks)	-5 to -3 ⁴	-5 to -3 ⁴	-2 to -1	1	2	4	8	12	14
Time point (Days)	-33 to -26	-30 to -23	-9 to -4	1	14 (±2D)	28 (±2D)	56 (±2D)	84 (±2 D)	98 (±2 D)
Informed consent	X								
Assess eligibility criteria	X ⁵	X		X ⁶					
Demographics	X								
Medical history	X								
Physical examination	X								
Height	X								
Weight, BMI	X			X	X	X	X	X	X
Tophi assessment	X								X
Pregnancy test ⁷	X ⁸			X	X	X	X	X	
Hep B, Hep C, HIV test	X								
Record prior ⁹ /concomitant medications	X		X	X	X	X	X	X	X
12-lead ECG	X			X					X
Vital signs	X ¹⁰		X	X ¹¹	X	X	X	X	X
Blood sampling for endpoints and laboratory tests	X ⁴		X ⁵	X ¹²	X	X	X	X	
Blood sampling for PK/PD ¹³				X	X	X	X	X	
Urine sampling - urinalysis	X		X	X	X	X	X	X	
sUA blood sampling for randomization			X ⁵						
Randomization				X ^{14,15}					
Dispense prophylaxis ¹⁶		X		X		X	X		
Dispense study drug				X		X	X		
Collect unused prophylaxis				X		X	X	X	
Collect unused study drug						X	X	X	
Drug accountability/compliance				X ¹⁷		X	X	X	
Assess and record adverse events	X	X	X	X	X	X	X	X	X
Gout Flare eDiary ¹⁸		X ¹⁹	X	X	X	X	X	X	
eDiary device return									X

¹. Subjects will be instructed to attend all Visits following a fast for at least 8 hours except visit at Day 98 (Visit 9).

². All efforts should be made to maintain protocol-defined visit windows, but if an extenuating circumstance arises preventing this, the Sponsor and/or designee should be consulted. If the Sponsor and/or designee determine that the scientific integrity of data and subject safety would not be compromised, an out of window visit may be permitted.

³. Subjects will be instructed to withhold the investigational products on Visit days.

⁴. Screening Visit will be between Day -33 to -26; prophylaxis will start between Day -30 to -23, once a subject is confirmed eligible. Subjects will be instructed to discontinue their current ULT the same day they begin prophylaxis if they are on ULT at screening.

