mg. In the multiple ascending dose (MAD, once daily doses for 7-days) study, subjects were administered placebo, febuxostat 80 mg, or LC350189 100 to 800 mg. There were no deaths, serious adverse events (SAEs), severe adverse events (AEs), or discontinuations due to AEs, and no clinically significant AEs. Specifically, in the SAD study, among subjects administered LC350189 10 mg (n=6), one subject experienced back pain; among subjects administered LC350189 25 mg (n=6), one subject each experienced nasal congestion or sneezing; among subjects administered LC350189 100 mg (n=8), one subject each experienced flushing or headache; and among subjects administered LC350189 200 mg (n=8), one subject each experienced diarrhea, feeling hot, headache, nasal congestion, rhinorrhea, or throat irritation. In the MAD study, among subjects administered LC350189 100 mg (n=8), one subject experienced hematochezia; and among subjects administered LC350189 600 mg (n=8), one subject each experienced diarrhea, flatulence, lip ulceration, or nausea.

Systemic exposure to LC350189 increased with increasing dose in both the SAD and MAD studies, with no significant differences in pharmacokinetic (PK) properties between studies. The range of time to reach maximum plasma concentration (t_{max}) of LC350189 was 1.0 to 6.0 hours after dosing in the SAD study and 1.0 to 5.0 hours in the MAD study, and elimination half-lives were 5.1 to 15.0 hours and 8.6 to 13.8 hours in the SAD and MAD studies, respectively. In the MAD study, steady state was reached after approximately 2 to 3 days. To evaluate the effect of a high-fat diet on the PK profile of LC350189, the PK with a high-fat diet was compared in the 200 mg dose level group. A high fat diet decreased maximum plasma drug concentration (C_{max}) to 62% of the fasting C_{max} , but no significant change in area under the curve (AUC) was observed after food intake. The sUA 24-hour mean serum concentration ($C_{mean,24}$) on Day 1 decreased by 8.7 to 31.7% from baseline in the SAD study. In the MAD study, the decrease in sUA reached steady state on Day 5 in the 100 mg, 200 mg and febuxostat groups, and on Day 6 in other dosage groups, and the percentage decreases in the sUA $C_{mean,24}$ ranged from 53.5 to 91.2%, while that of febuxostat 80 mg was 58.8% on Day 7. The percentage changes in sUA increased with higher doses, and the changes in all dose groups except for 100 mg were statistically different from that of the febuxostat group.

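### Protocol 8.4.1 allows withdrawal from the study for non-compliance without requiring a Day 84 sUA, so the primary analysis can score as a failure a subject who could still have been sampled

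*Protocol*

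**What the plan says.** Protocol 8.4.1 defines persistent non-compliance as use below 80% or above 120% since the last visit. It then says that "it may be appropriate to withdraw the subject from the study". The next sentence asks that all subjects be re-instructed on dosing at visits.

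Protocol 6.4.3 gives two further discretionary routes out. One is a protocol violation that could interfere with the drug or affect safety, where "the subject will be withdrawn by the Investigator". The other reads "Subject conduct or any other events, which, in the clinical judgment of the Investigator or after discussion with the Sponsor, may invalidate the study".

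Three places bear on sampling after exit:

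- 6.4.3, closing text: "Wherever possible, the tests and evaluations, including those listed for the follow-up Visit (Visit 9), should be performed for all subjects who discontinue".
- 6.4.3, consent-withdrawal paragraph: "Subjects will be encouraged to continue all study assessments".
- Table 2-1: the Visit 8 column is also the early-termination visit. No blood sampling is marked at Visit 9.

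The primary endpoint is sUA below 5.0 mg/dL at Day 84. Protocol 12.2.3 and SAP 8.1 apply non-responder imputation (NRI) to dropouts. SAP 8.1.1 keeps every Day 1 subject in the denominator. For this endpoint, last observation carried forward (LOCF) appears only in the SAP 8.2 sensitivity analysis. Withdrawn subjects are not replaced (Protocol 6.1).

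**The concern.** NRI is a sound rule for values that cannot be obtained. Here the value may be obtainable. The subject has not withdrawn consent and may be willing to attend, yet the investigator may end participation, and the analysis then records a failure that nobody observed.

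Placebo response is expected to be near zero, so the loss falls mainly on the active arms. The primary objective is to find the therapeutic dose, and Protocol 12.4 kept 38 per group for dose selection. The response rate at each dose is therefore what the trial is meant to deliver.

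**Working it through.** **1. Is a Day 84 value secured anywhere?** No.

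- The closing text of 6.4.3 applies to everyone who discontinues, but only where possible. It names Visit 9, which has no blood draw.
- The early-termination use of Visit 8 gives a sample on the day of exit, not at Day 84.
- The encouragement to continue assessments sits in the consent-withdrawal paragraph and is not a requirement.

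**2. When would withdrawal occur?** In Table 2-1 the row "Drug accountability/compliance" is marked at Visits 4, 6, 7 and 8, and a footnote limits Visit 4 to colchicine. Study-drug compliance is thus first counted at Day 28 and next at Day 56. Persistent non-compliance points most naturally to Day 56, which leaves one treatment visit (Visit 8). From Day 28, two would remain.

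**3. The plan's own figures (Protocol 12.4).**

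- n = (1.96 + 0.84)² × (0.80×0.20 + 0.47×0.53) / (0.80 − 0.47)² = 7.84 × 0.4091 / 0.1089 = 29.45, so 30.
- With 20% dropout: 30 / 0.8 = 37.5, so 38.
- Power for 0.80 vs 0.10 at n = 30: z = 0.70 / √(0.25/30) − 1.96 = 5.71, so above 99.9%.

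All three match. No stated figure is wrong.

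**4. Loss in one arm.** Let k be the number of subjects withdrawn and r the share of them who would be below 5.0 mg/dL at Day 84. Neither is in the documents; r = 0.25 to 0.50 is assumed for non-adherers who stay on drug. The loss is k × r / 38.

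| k | r = 0.25 | r = 0.50 |
|---|---|---|
| 1 | 0.7 points | 1.3 points |
| 3 | 2.0 points | 3.9 points |

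One certain responder lost costs 1/38 = 2.6 points.

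**5. Difference from placebo, three withdrawn in every arm.** The change is 3 × (r active − r placebo) / 38. It runs from 3 × (0.25 − 0.10)/38 = 1.2 points to 3 × (0.50 − 0)/38 = 3.9 points.

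**6. Power.** With three per arm set to failure, the expected rates at 0.80 vs 0.10 become 28/38 = 73.7% and 3.5/38 = 9.2%. Exact binomial power of the Wald 95% interval stays above 99.9%.

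**7. Dose ranking.** Assume true rates of 80% and 70%, 38 per arm. The table gives the exact binomial probability that the better dose has the strictly higher observed rate.

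| Three withdrawals in | Scored as failures | Measured, r = 0.25 | Measured, r = 0.50 |
|---|---|---|---|
| both arms | 0.798 | 0.789 | 0.786 |
| better arm only | 0.60 | 0.67 | 0.74 |

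**8. Subjects off drug.** Protocol 4.3 reports that "elimination half-lives were 5.1 to 15.0 hours and 8.6 to 13.8 hours in the SAD and MAD studies, respectively". From Day 56 to Day 84 is 28 × 24 / 13.8 = 48.7 half-lives at the longest multiple-dose value, and entry sUA is at least 8.0 mg/dL. If such subjects respond like placebo (0 to 10% in Protocol 12.4), sampling three of them recovers 0 to 3 × 0.10/38 = 0.8 points.

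**The case against.** The strongest reply is that no planned conclusion changes. Power is untouched. With equal withdrawals, ranking is marginally better under the present rule. Counting a subject removed for not taking the drug as a failure is coherent, conservative and pre-specified. The rule is discretionary and already paired with re-instruction. A subject leaving at Visit 7 has a scheduled Day 56 sUA, and in phase I the decrease in sUA reached steady state by Day 5 or 6, so that value is a fair proxy for Day 84 on drug. SAP 8.2 carries it forward. Response at each visit, change from baseline with LOCF and the per-protocol analysis also inform dose choice. The 20% dropout allowance (about 8 of 38) covers three withdrawals.

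Most of this stands, and it makes the point small. It does not remove it: the primary estimate still scores an unobserved failure, and LOCF does not supply a Day 84 measurement.

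Three stronger readings are tempting, and the documents do not support them.

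- **Dose selection is compromised.** This needs uneven withdrawals, such as all three in the better arm. Nothing in either document points to that.
- **The 6.4.3 withdrawal bullets need the same restriction.** The protocol-violation bullet also covers subject safety, and an exception could weaken it.
- **Over-use is capped at 125%, so continuing drug is harmless.** Bottles are described as "each containing 35 capsules", and 35/28 = 125%. But Day 1 to Day 28 is 27 days by the SAP 7.2.2 date difference, giving 35/27 = 130%. With the ±2-day windows, Day 1 to Day 26 gives 35/25 = 140%, and Day 30 to Day 54 gives 35/24 = 146%. These are interval averages, not limits on a daily dose.

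**Conclusion.** The point holds as a cheap improvement, not as a flaw that threatens the trial. An optional removal can create a missing primary value, and no text requires the sample that would prevent it.

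The likely bias is about 2 to 4 points in an arm's response rate per three withdrawals. That rests on two assumptions outside the documents: the number withdrawn, and a 25% to 50% response among non-adherers who stay on drug. The gain is confined mainly to subjects who continue taking drug. The comparison with placebo is safe at the planned rates. A reader should not infer that NRI is the wrong rule here; it remains right for subjects with no Day 84 value.

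**What to change.** In Protocol 8.4.1, replace the withdrawal sentence with:

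*Non-compliance alone is not a reason to withdraw a subject from the study. Re-instruct the subject and record the deviation. Study drug may continue unless the Investigator judges there is a safety concern (including use >120%), in which case drug is stopped; in either case the subject is asked to continue scheduled assessments through the Visit 8 (Day 84) sUA sample.*

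Leave the 6.4.3 bullets unchanged, including the safety limb of the protocol-violation bullet. Keep NRI for subjects with no Day 84 value.

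**Cost.** The change is wording in one protocol section and one already scheduled visit per affected subject (two if the problem is found at Day 28). It adds no procedure and needs no SAP amendment.

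**Downside.** The full-analysis-set rate will include responses under imperfect adherence. The compliance cutoff that SAP 4.4.4 leaves to the blinded data review handles this in the per-protocol analysis. That meeting should confirm that the cutoff takes precedence over the sentence in 4.4.4 that includes completers with an sUA within 5 days of Day 84.
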